The products of Aim 1 will be: (1) a comprehensive taxonomy of types and features of telemedicine offered in response to the COVID-19 pandemic; (2) a nuanced understanding of the perspectives of those seeking to use telemedicine, including advantages and disadvantages, facilitators and barriers, and perceived value; and (3) stakeholder-informed input for use in Aim 2 analyses, including details of site characteristics and telemedicine interventions as well as outcomes prioritized by stakeholders.

Data Sources

This will be a primary data collection using telephone interviews, for which participants will receive a stipend of \$40.

Data collection: For both patients and providers, semi-structured interview instruments will be designed to explore experiences with, advantages and disadvantages of, and barriers to and facilitators of telemedicine. The interview guides will be finalized with input from the Stakeholder Advisory Board and pilot tested for clarity. Trained interviewers will

PRINCIPAL INVESTIGATOR: [name]; [name]

conduct 30- to 45-minute individual interviews in English or Spanish. All interviews will be audio-recorded and professionally transcribed.

Confidentiality and Data Management: As stated in the PCORI Methodology Standards, researchers have an obligation to ensure confidentiality.⁶ All personally identifiable data will be redacted during transcription, and the code list linking transcripts to participant identity and consent forms will be stored separately and accessible only to the site PI. Audio recordings will be stored on protected servers accessible only to the site PI and team and will be destroyed after data analysis is complete.

Sample

We will recruit both patients and providers from primary care clinics that transitioned to telemedicine to ensure representation from individuals who have had experience with the technology. Both PCPs and patients will help us understand the features of telemedicine utilized (e.g. synchronous video, telephone calls) and their relative experiences with these features. Our approach to sampling PCPs from different practices and purposive patient sampling serves our goal of understanding telemedicine experience by diverse populations.

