Aim 1A quantitative results will be summarized with descriptive statistics. Bivariate analyses will be conducted to assess association of telemedicine features with practice characteristics. In addition to a taxonomy based on the Triangle Model and the Penchansky and Thomas access to care framework,^{2,3} we will also explore a data-driven approach to a taxonomy of implemented telemedicine programs. Here, a 3-step approach will be followed applying two separate data reduction techniques as previously described.⁹ First, multiple correspondence analysis¹⁰ will be applied to study relationships between the (categorical) items in each of the seven conceptual domains of our survey. Where needed, continuous variables will be transformed into categorical variables; this will be distribution-based or based on natural cutoffs. In this step, for each of the seven domains, a select number of factorial axes will be retained for subsequent analyses. This will be based on the percentage of explained variance, interpretability, as well as visual representation of variables and organizations.¹¹ In the second step, the factorial axes that result from the multiple correspondence analysis will be integrated into a principal component analysis. Here, principal components will be retained based on a scree plot (visualizing the percent variance explained by the number of principal components) using the 'elbow criterion'.¹² In the third step, telemedicine programs will be classified using an ascending hierarchical classification method.¹³ This group partitioning technique involves minimizing intra-class variance and maximizing inter-class variance. To obtain the classification, we will inspect the resulting dendrogram (which represents the hierarchy tree) and the inertia quotient (interinertia/total inertia) graph. The latter typically visualizes increases in the inertia quotient (y-axis) with increases in the number of classes (x-axis). Here, we will select the number of classes based on the point after which any increase in the inertia quotient tends to level off. In addition to statistical considerations, decisions regarding the number of classes to retain will also take into account the interpretability of classes⁹. In other words, the number of partitions used in the final classification will take into account both the statistical criterion (inertia quotient) and the theoretical/clinical plausibility of the final groupings. All analyses will be conducted using SAS v.9.4 statistical software (SAS Institute, Cary, NC). These analyses will be conducted and overseen by coinvestigators [name] and [name] [name].

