Primary findings will be presented alongside descriptive statistics assessing the external and internal validity of the analysis, including balance across relevant covariates before and after matching. We will also use descriptive statistics to characterize the analysis population, identify sources of missingness in the data across outcomes and covariates as well as whether missingness may introduce selection bias into our analysis. In sensitivity analyses, we will multiply impute covariates for which there is meaningful evidence of missingness.

Heterogenous Treatment Effects

We hypothesize that patients in disadvantaged sociodemographic groups will derive less benefit from telemedicine than patients in majority groups because of barriers to use of telemedicine described in the conceptual model. We additionally hypothesize that more robust telemedicine programs (as defined in the Aim 1 taxonomy) will provide more benefit to patients than less robust ones.

We will explore variation in effects for the outcomes listed in Table 1 among pre-specified sociodemographic subgroups (race/ethnicity, rurality, median income for zip code) and clinical subgroups (COVID-19 patients vs. all other patients; low vs. high burden of illness; stable vs. unstable disease, as indicated by clinical measures of disease progression). Finally, we will use the Aim 1 survey for stratified analyses of telemedicine factors, such as historical use of telemedicine and patient technical assistance. Additionally, the Medicare data will allow us to conduct a subgroup analysis for our claims-based outcomes on dually eligible patients. Therefore, we will conduct eight separate subgroup analyses in all. We will use the same analytic approach described in the primary analysis to conduct these subgroup analyses and present the differences in treatment effect estimates with standard errors. We will also conduct univariate subgroup analyses with interaction effects to statistically test for differences in outcomes (as outlined below) among these subgroups.

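### The rule for choosing the number of telemedicine program classes will usually return two or more even where practices do not group, and nothing checks that the classes reproduce

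*Combined protocol and SAP*

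**What the plan says.** Section D, Analytic Methods, builds the data-driven taxonomy for Aim 1A in three steps.

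- **Multiple correspondence analysis by survey domain.** The plan states that "for each of the seven domains, a select number of factorial axes will be retained for subsequent analyses". The number is not fixed.
- **Principal component analysis of those axes.** Components are kept by a scree elbow.
- **Ascending hierarchical classification.** "This group partitioning technique involves minimizing intra-class variance and maximizing inter-class variance". The team inspects the dendrogram and "the inertia quotient (interinertia/total inertia) graph", and "we will select the number of classes based on the point after which any increase in the inertia quotient tends to level off".

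The plan adds that "decisions regarding the number of classes to retain will also take into account the interpretability of classes", so that the final partition reflects "both the statistical criterion (inertia quotient) and the theoretical/clinical plausibility of the final groupings".

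The approach is introduced as exploratory, next to a taxonomy built on two existing frameworks. Section C (Overview) lists as the first product of Aim 1 "a comprehensive taxonomy of types and features of telemedicine offered in response to the COVID-19 pandemic". Section F (Heterogenous Treatment Effects) hypothesises that "more robust telemedicine programs (as defined in the Aim 1 taxonomy) will provide more benefit to patients than less robust ones", without saying which taxonomy is meant. Section F (Primary Analysis) separately defines a composite robustness score from the survey.

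**The concern.** The statistical part of the rule looks only at how the quotient grows. A quotient that starts at zero, never falls and is bounded by one must flatten somewhere, so the graph offers a stopping point whether practices form distinct groups, lie along a continuum or show no association at all. Interpretability and plausibility help to decide how many classes to keep; they are not a test that classes exist. The text available contains no stability check, no single-class reference and no stated outcome in which the team concludes that there are no distinct types. The trustworthiness safeguards in Section D (audit trail, member checks) belong to the Aim 1B interviews.

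At stake is whether the published types would be found again in another sample of practices. If the classes were used to grade program robustness in Aim 2, unstable classes would also misclassify practices there.

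**Working it through.** The plan gives no expected number of classes, threshold or error rate for this step, so there is no figure to reproduce.

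**Algebra.** With between-class inertia B(k), within-class inertia W(k) and total T = B(k) + W(k), the quotient is Q(k) = B(k)/T. Splitting a class into parts of size n1 and n2 with centroids c1 and c2 raises B by n1·n2/(n1 + n2) × |c1 − c2|², which is never negative. So Q(1) = 0, Q(k+1) ≥ Q(k) and Q(k) ≤ 1 for any data.

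**Simulation inputs.** From the plan: 250 practices (Section C, Sample); seven domains with 6, 3, 8, 2, 17, 1 and 2 items, 39 in all (counted from Appendix A); the three steps above. Assumed: 2 or 3 levels per item, two axes per multi-item domain, Ward linkage, and a latent loading of 0.6 for the gradient. There were 200 data sets per scenario.

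**Mean quotient for k = 1 to 6, with gains in percentage points.**

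- Independent items: 0, 0.185, 0.322, 0.410, 0.472, 0.519; gains 18.5, 13.7, 8.8, 6.2, 4.7.
- One continuous gradient, no groups: 0, 0.496, 0.670, 0.751, 0.803, 0.837; gains 49.6, 17.4, 8.1, 5.2, 3.4.
- Three real groups: 0, 0.506, 0.935, 0.946, 0.954, 0.960; gains 50.6, 42.9, 1.1, 0.8, 0.6.

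**Share of data sets giving two or more classes (range of k), under four readings of levelling off.**

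| Reading | Independent | Gradient | Three groups: exactly 3 |
|---|---|---|---|
| Greatest distance from chord | 100% (3–6) | 100% (2–4) | 100% |
| Largest drop in gain | 100% (2–7) | 100% (2–3) | 100% |
| Last gain of at least 5 points | 99.5% (1–7) | 100% (3–6) | 99.5% |
| Last gain of at least 10 points | 71.5% (1–4) | 100% (2–4) | 100% |

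The first two readings cannot return one class by construction, so their 100% carries no information beyond the algebra. The two threshold readings can. The strictest gave one class in 57 of 200 independent-item data sets (28.5%).

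**Sensitivity.** With 1 to 3 axes and 2, 3, 5 or 8 components (100 data sets per setting), two or more classes appeared in 99% to 100% everywhere, with one exception: the 10-point reading with 8 components and independent items gave one class in every run. Retention matters: with two axes and independent items, mean Q(2) falls from 0.31 with 2 components to 0.07 with 8.

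**Do the classes reproduce?** Median adjusted Rand index on bootstrap samples (60 data sets per scenario): 0.11 for independent items, 0.49 for the gradient, 1.00 for three groups. A second simulation with slightly different item counts (2 to 4 levels, chord reading) gave 3 to 6 classes in all 300 independent-item data sets. Rerunning on 80% subsamples (200 of 250 practices) gave a mean index of 0.14, against 0.997 with three real classes.

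**Would a null comparison help?** A gap-type comparison with a multivariate-normal reference returned one class in 58 of 60 independent-item data sets but only 24 of 60 gradient data sets (40%), and three classes in 60 of 60 with three groups. Permuting each item independently does not serve: gradient-only data passed in 30 of 30 data sets at each of the loadings 0.4, 0.6 and 0.8, because permutation tests for any association rather than for discrete groups.

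**The case against.** The strongest defence is that this is an exploratory, descriptive step, and segmenting a continuum can be legitimate description. The elbow is judged by eye, alongside the dendrogram and plausibility, so a team could decline classes that make no sense. Fully independent items are also unrealistic: Appendix A lists patient mix and trainee status under two domains each, so some dependence is built in.

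Much of this stands. It limits the consequence, but supplies no check of reproducibility. The gradient scenario, which answers the point about dependence, gave two or more classes under every reading.

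A reader might infer two stronger things that the documents do not support.

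- **That the rule can never return a single class.** The plan fixes no numeric elbow, a strict reading sometimes returns one class, and plausibility judgements could lead to the same result.
- **That Aim 2 contrasts are diluted.** No section says that cluster membership enters an Aim 2 model. The composite score is a separate route to robustness, Section F also stratifies by individual survey features, and the reference to the Aim 1 taxonomy could mean the framework-based one. No dilution has been calculated.

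**Conclusion.** The point holds as a minor gap. The rule finds well-separated groups reliably, but it cannot tell them from no groups or from a continuum, and the plan has nothing that would reveal the difference. Without grouping, two or more classes are the usual result: 71.5% to 100% with independent items, depending on how the elbow is read, and 100% with a gradient. The single departure was the strict reading with 8 components.

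The consequence falls on the exploratory data-driven taxonomy. It reaches Aim 2 only if these classes are used to define program robustness. The percentages rest on assumed item levels, retained axes, gradient strength and numeric readings of a visual rule. The monotone quotient does not depend on those assumptions.

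**What to change.** In the third step of Section D, Analytic Methods, add the following.

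1. Rerun all three steps on bootstrap samples or 80% subsamples, and report the adjusted Rand index for the chosen number of classes.
2. Prespecify a threshold for that index. A value such as 0.6 is only an illustration: in 30 gradient-only data sets per loading, the index fell below it in 93% at loading 0.6, but 70% met it at loading 0.8. A strong continuum can therefore pass.
3. Unless the threshold is met, present the classes as a descriptive segmentation rather than distinct types, and use the framework-based taxonomy and composite robustness score in Aim 2. State in Section F which taxonomy the robustness hypothesis means.
4. If a null comparison is added, use a single-cluster reference that keeps the correlation between items, such as the gap-type comparison above, not independent permutation of items. State that it only partly separates a continuum from true groups.

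The cost is a few hours of computing on data already being collected and a few sentences of text. The downside is that the data-driven taxonomy may turn out not to be supported as discrete types.

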This study will provide rapid, actionable guidance about the comparative effectiveness of telemedicine relative to in-person visits for primary care chronic disease management, and about organizational implementation choices that support telemedicine effectiveness. Our findings will provide patients, providers, and policymakers with rigorous evidence about alternative models of health care delivery in a time of innovation, expansion, and development of telemedicine.

C. AIM 1 METHODS: PARTICIPANTS, INTERVENTIONS, OUTCOMES

Overview

Because the COVID-related transition to telemedicine was so abrupt and universal, there is little existing evidence on barriers to and facilitators of telemedicine implementation in primary care from either patient or provider perspectives. In this phenomenological study,¹ we will conduct inductive research informed by the voices of the participants, in the absence of relevant existing social theory.

Aim 1A is a telephone survey of primary care practice leadership to collect nuanced information about sites and characteristics of telemedicine initiatives. The 15-minute survey will cover characteristics of the sites and of the telemedicine offerings, including features, implementation processes, workflows, technical support, integration of interpreter services, and related programs such as remote patient monitoring. Preliminary survey domains and scales (see **Appendix A**) are guided by the Triangle Model and the Penchansky and Thomas access to care framework.^{2,3}

Aim 1B is a qualitative interview study with patients and primary care providers (PCPs). Interviews will explore experiences, advantages and disadvantages of telemedicine, and barriers to and facilitators of telemedicine. A clinical research coordinator will administer informed consent and trained interviewers will conduct 30-45-minute interviews in English or Spanish.

For both studies, the interview instrument will be finalized with input from stakeholders (see Engagement section) and pilot tested. The semi-structured format allows detailed, complex data to be categorized later, improves engagement to optimize response rate, and minimizes risk of social desirability response bias.^{4,5}

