For Aim 1A, we will use two sampling frames. First, we will survey one leader at each eligible adult primary care practice within the CRNs participating in Aim 2 (INSIGHT, OneFlorida, and STAR). The target sample size of practices is 250 practices. If our total sample size does not reach 250, or if we want to do targeted recruitment for specific practice types, we will draw additional primary care practices nationally using an Agency for Healthcare Research and Quality file of group practices.⁷

For Aim 1B, we will recruit PCPs from both sampling frames with experience using or attempting to use telemedicine, sampling for maximum variability across practice environments (e.g., high vs. low Medicaid patient share), locations (e.g., urban vs. rural), and clinical roles. We will recruit adult patients (English or Spanish speaking) with a chronic condition under study who have attempted to use or have used telemedicine. We will recruit patients through our participating CRNs, a patient registry at Mount Sinai (REMIND study (HS: 15-00792) and through provider nominations. We will conduct purposive sampling on the basis of age, primary language, insurance type, illness severity, and location. The target sample size is 75 patients and 25 providers.

In our inductive approach (see analysis section below), we will iteratively conduct interviews and analyze data until the team concurs that thematic saturation has been reached (when new interviews cease to yield new concepts).⁸ In addition, during the analysis, we will also critically assess our participant sampling selection to identify additional participants to interview to reflect specific perspectives or viewpoints. Although this means we cannot establish a precise sample size *a priori*, we conservatively plan for 25 PCPs and 75 patient interviews.

The advantage of using thematic saturation as a stopping criterion is that it allows us to avoid establishing a fixed sample size *a priori* in order to be able to respond flexibly to the data collection and analysis process.^{1,8} Using this approach, we plan to continue sampling and analyzing the data until we reach saturation. This means that we can increase the sample size of PCPs to more than 25 if we determine it is needed. (In addition, we can also increase or reduce the patient sample size, currently estimated at 75, if needed.)

Outcomes and Covariates

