For Aim 1A, primary outcomes and covariates to be collected will be start and end dates of implementation of telemedicine programs at the sites, features of the telemedicine programs launched including type of platform used and

PRINCIPAL INVESTIGATOR: [name]; [name]

availability of technical support and training, and characteristics of the practice site including ownership, pre-COVID-19 experience with telemedicine, and type of patient population served. See Appendix A for more details.

For Aim 1B, patients and providers will be asked about their experiences with telemedicine and whether it has been successful or unsuccessful, their attitudes toward telemedicine, and their perceptions. Covariates to be collected include demographics, previous experience with telemedicine and information technology, and location.

D. AIM 1 METHODS: DATA COLLECTION MANAGEMENT, ANALYSIS

Analytic Methods

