The study population encompasses patients that are attributed to primary care clinics in one of the four health systems defined above. Patients are included in the study if they are ages 19 or older and received two or more outpatient visits at a participating practice during a one-year period before the COVID-19 pandemic, and had one or more of five chronic illnesses (asthma, chronic obstructive pulmonary disease (COPD), congestive heart failure (CHF), diabetes, hypertension) as defined by the Medicare Chronic Conditions Warehouse algorithm.²⁷ For the claims analyses, we additionally require that patients are continuously enrolled over the entire study time period.

Interventions and Comparators

We will use natural variation in the availability of in-person and telemedicine visits across clinics over time during the pandemic in a difference-in-differences framework to compare the clinical effectiveness of three care models: (1) telemedicine-only; (2) telemedicine-supplemented in-person visits; and (3) in-person visits only.

While these arms will be defined at onset of the pandemic, clinics may not remain in the same arm over time. We will evaluate changes in total telemedicine and in-person visits in each month and capture the status of each clinic by month for secondary analyses. In additional secondary analyses, we will explore heterogeneity in effects across patient and organizational subgroups.

The intervention population encompasses patients that are attributed to primary care clinics that switched to delivering telemedicine-only visits as their primary model of care delivery during the pandemic. We will compare this population to patients that are attributed to clinics that delivered telemedicine-supplemented in-person visits or in-person visits only during the pandemic. We will define the clinics' primary model of care delivery, and the timing of their switch in clinical modality, using the survey results from Aim 1.

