**After submission of this grant, the three participating CRNs agreed to begin collecting data that would allow us to distinguish between telemedicine and in person visits, an item that was not available when this study was designed. This may enable us to conduct a separate analysis of telemedicine versus non-telemedicine visits at the visit level.*

Finally, we will collect PROs using REDCap surveys through the WCM REDCap database. REDCap is a secure website for building and managing online surveys and databases. It is available at each site and harmonized across institutions to facilitate data storage and management. REDCap will generate automated emails or text messages to patients containing hyperlinks to access surveys. The REDCap team will be responsible for maintenance during the study period. Table 4 summarizes the primary data sources and data elements.

Table 4

Data Sources	Data Elements
Medicare, Commercial claims, CRN structured EHR data	Diagnosis codes
Medicare, Commercial claims, CRN structured EHR data	Procedure codes
Medicare, Commercial claims, CRN structured EHR data	Demographic characteristics
Medicare, Commercial claims, CRN structured EHR data	Health care utilization
Commercial claims, CRN structured EHR data	Laboratory testing results
Medicare, Commercial claims, CRN structured EHR data	Medications
REDCap surveys	Patient experience and satisfaction

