We will define the degree of telemedicine exposure (dose) in two ways. First, based on the comprehensive landscape survey of primary care leaders in [Aim 1](#), we will develop a composite score indicating the robustness of the telemedicine program at each clinic site under study. Among other features, this score will take into account the total number of components and delivery modes of the telemedicine program, its focus on providing coordinated care to a patient population with chronic care needs, and staff and clinical support from the organization.

Second, we will define telemedicine exposure based on the proportion of all visits at a given clinic that are delivered via telemedicine in each month. Specifically, we will classify clinics into quartiles of telemedicine exposure based on the distribution of all telemedicine provision among clinics in this treatment arm. We will then separately analyze the relationship between our outcomes of interest and the amount (dose) of telemedicine being offered at a clinic. We will cluster all primary and secondary analysis at the clinic level, as this is the level at which the exposure occurred.⁴³

Finally, in addition to the primary intent-to-treat analysis, we are proposing an additional secondary analysis. This secondary “as treated” analysis is designed to evaluate the relationship between patient-level telemedicine exposure and our outcomes of interest. In this secondary analysis, we will characterize patients’ exposure to telemedicine after the first wave of shelter-in-place measures were put into place based on the treatment that they actually received

PRINCIPAL INVESTIGATOR: [name]; [name]

rather than based on the availability of telemedicine at the primary care clinic to which they were attributed. In this analysis, we will adjust for observed clinic and patient-level characteristics as described in the response above that may impact both the availability and choice to use telemedicine, as well as patient outcomes. Additionally, we will provide estimates from a fixed effects model in which each patient serves as their own control.

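### Clinic arm and switch date rest on a one-leader survey, with no check against the planned monthly visit counts and no rule for clinics that do not answer

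*Combined protocol and SAP*

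**What the plan says.** Section E, Interventions and Comparators, defines three clinic-level care models, with arms set at the onset of the pandemic. It takes each clinic's model, and "the timing of their switch in clinical modality, using the survey results from Aim 1".

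Section C describes that survey. On sampling: "we will survey one leader at each eligible adult primary care practice within the CRNs participating in Aim 2". On length and content: "The 15-minute survey will cover characteristics of the sites and of the telemedicine offerings". The date item listed under Outcomes and Covariates is "start and end dates of implementation of telemedicine programs at the sites".

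The plan also has a visit-based measure of the same exposure. Section E states: "We will evaluate changes in total telemedicine and in-person visits in each month". It will also "capture the status of each clinic by month for secondary analyses". Section F, Primary Analysis, uses "the proportion of all visits at a given clinic that are delivered via telemedicine in each month" to form dose quartiles. Section F, Data Collection Methods and Data Sources, adds that after the grant was submitted "the three participating CRNs agreed to begin collecting data that would allow us to distinguish between telemedicine and in person visits". It mentions this only as something that might support a separate visit-level analysis.

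Outcomes are patient-month measures read at 30 days, 60 days, 6 months and 1 year after exposure (Section E, Outcomes and Participant Timeline). The primary model is an event study that compares clinics by when they switched (Section F, Primary Analysis).

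**The concern.** The primary estimate depends on two facts per clinic: its arm and its switch month. Each comes from one respondent. The text available contains no comparison with visit data, no visit-share cut-off separating the three arms, and no rule for a clinic whose leader does not respond.

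Three things are at stake.

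- **Timing.** The switch month sets time zero of the event study. If it is wrong, pre-switch months are counted as exposed, or exposed months as baseline. The shortest outcome windows suffer most.
- **Arm.** Clinics are matched on initial arm status, so an arm error carries into the matching as well as the contrast.
- **Clinic loss.** Non-response removes whole clinics. If the silent clinics differ from the others, the loss is selective as well as a loss of size.

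**Working it through.** **1. The plan's nearest figure.** The plan gives no number for date error, arm error or survey response. The closest stated figure is the non-inferiority power for the ED outcome in Section E, Power Calculation: 25,000 per arm, ED rate 20% to 5%, margin 1 percentage point, one-sided 2.5%, power 80% to 99%.

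Power = Φ(0.01 / √(2p(1−p)/n) − 1.96)

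- p = 0.20: 0.01 / √(0.32/25,000) = 2.795; Φ(2.795 − 1.96) = 79.8%.
- p = 0.05: 0.01 / √(0.095/25,000) = 5.130; Φ(5.130 − 1.96) = 99.9%.

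The stated range reproduces and is not in dispute.

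**2. Effect of a wrong switch date.** If the reported date is m days off in either direction, a W-day window shares max(0, 1 − m/W) with the true window. The values of m are assumptions.

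| Date error m | 30 days | 60 days | 6 months (182 d) | 1 year (365 d) |
|---|---|---|---|---|
| 7 days | 77% | 88% | 96% | 98% |
| 15 days | 50% | 75% | 92% | 96% |
| 30 days | 0% | 50% | 84% | 92% |
| 60 days | 0% | 0% | 67% | 84% |

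Because outcomes are built by patient-month, an error at that resolution is at least one month, which is the third row: 1 − 30/30 = 0; 1 − 30/60 = 0.50; 1 − 30/182 = 0.835; 1 − 30/365 = 0.918.

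**3. What happens to a clinic that does not answer.**

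- Section C, Sample, responds to a shortfall below 250 practices by drawing practices from a national file.
- Section E, Study Setting and Eligibility Criteria, limits Aim 2 to patients attributed to clinics in four health systems. An added national practice therefore cannot supply an arm for a silent Aim 2 clinic.
- Section F, Missing data, names non-response to the REDCap patient survey but not to the Aim 1A survey. For claims sources it prescribes listwise deletion.

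On this text the clinic has no arm and drops out.

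**4. Effect of clinic loss on precision.** As an illustration only, suppose the 25,000 per arm shrinks in proportion to an assumed response rate. At 70% response and p = 0.20, n = 17,500 and 0.01 / √(0.32/17,500) = 2.339, so Φ(2.339 − 1.96) = 65%.

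| Assumed response | Power, ED rate 20% | Power, ED rate 5% |
|---|---|---|
| 90% | 76% | 99.8% |
| 70% | 65% | 99% |
| 50% | 51% | 95% |
| 30% | 33% | 80% |

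These figures ignore clustering by clinic. The plan calls 25,000 a minimum. If arms start larger, 25,000 may survive the loss, and selection becomes the main issue.

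**The case against.** The strongest defence is that the survey rule is deliberate. Section E explains that patients who choose telemedicine differ from those who do not, so the primary exposure is what the clinic made available, analysed by intention to treat. Realised visit mix also reflects patient demand. Section F therefore keeps visit share for dose, and care actually received for a separate as-treated analysis. This stands. A reader might infer that visit counts should replace the survey as the primary definition, but the documents do not support that. An assignment window in the first months would overlap the 30- and 60-day outcomes. Medicare fee-for-service claims show only part of a clinic's visits. Claims sources are analysed separately, so one clinic could receive different arms in different data sets.

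Other stronger readings also fail.

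- **Dates are poorly recalled.** No survey date is given, and nothing says leaders answer from memory. The IRB exemption of 11/16/2020 and the April 2020 peak suggest a gap of about seven months, but that is an inference. The plan describes the transition as abrupt, which may make dates easier to pin down.
- **The survey needs dates when in-person care resumed.** Primary arms are fixed at onset, so later changes belong to the monthly-status analyses. Appendix A lists preliminary topics, so an item without a date there proves nothing about the final question.
- **CRN modality data solve the problem.** The CRNs agreed to begin collecting it; nothing shows that it reaches back to spring 2020.
- **A count of patients lost can be stated.** Applying an assumed response rate to the 205,867 patients in Table 2 would mislead. That table includes some specialty patients, and the primary analysis is of Medicare claims.

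The monthly-status, re-matching, dose and as-treated analyses soften the problem. None of them checks the survey arm or gives a silent clinic an arm. Eligibility refers to a participating practice, which might be read as excluding non-responders. If so, the same clinics are lost at the eligibility step.

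**Conclusion.** The point holds in a limited form. The primary arm and switch timing rest on one survey answer per clinic, unchecked against counts the plan already produces, and non-responding Aim 2 clinics have no route into the primary analysis.

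The timing risk falls mainly on the 30- and 60-day outcomes: a one-month error would leave none of the first window and half of the second, against about 84% and 92% of the two longer ones. That is conditional on such an error occurring; the documents show only that it could go undetected. With no misclassification rate given, no size is claimed for dilution of the contrast between arms. With no response rate given, the power figures under clinic loss illustrate a range and are not forecasts.

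**What to change.** Keep the survey-based, availability-oriented arm as primary wherever a survey answer exists. Before outcomes are seen, write down visit-share cut-offs for the three arms and a rule for the switch month. Base both on each clinic's monthly telemedicine and in-person counts in claims, with CRN modality data added if they cover spring 2020. State the order of data sources so that a clinic carries one arm across all data sets. Then:

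1. assign arm and switch month by this rule to Aim 2 clinics that do not answer, so that they stay in the analysis;
2. report agreement between survey and visit data on arm and date, and resolve discordant clinics blind to outcomes;
3. repeat the primary analysis with visit-based arms and dates for all clinics, as a pre-specified sensitivity analysis.

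Report the Aim 1A response rate among Aim 2 clinics, with baseline characteristics of responders and non-responders.

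The cost is modest: the counts are already planned, so this adds a written rule, an agreement table and one further model run. The drawback is that clinics assigned by visits carry a delivery-based exposure, with the partial capture and early-window overlap described above. For that reason the visit-based version supplements the survey rule and does not replace it.
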